#### Surveillance/Survival Follow-up Phase

For the Surveillance/Survival Follow-up Phase of the study, an adverse event will be any event that starts following the start of the first dose of study drug for those subjects continued in the Surveillance/Survival Follow-up Phase of the study.

If the onset date and/or resolution date of an adverse event is incomplete (for example, only the month and year are available), the event will be assumed to start after the first dose of study drug,

---

as long as the available information does not conclusively indicate that the event emerged prior to the start date of the first cycle of study drug administration.

AEs in the Surveillance/Survival Follow-up Phase will be summarized and listed in the same form as aforementioned in the Neoadjuvant Atezolizumab Therapy Phase.

AE by highest NCI CTCAE grade will also be summarized for both study phases combined.

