##### Neoadjuvant Atezolizumab Therapy Phase

For the Neoadjuvant Atezolizumab Therapy Phase of the study, an adverse event will be any event that starts following the start of the first dose of study drug for those subjects not continuing in the Surveillance/Survival Follow-up Phase of the study, and through the day immediately preceding the start date of the first adjuvant cycle for subjects continuing in the Surveillance/Survival Follow-up Phase of the study.

---

If the onset date and/or resolution date of an adverse event is incomplete (for example, only the month and year are available), the event will be assumed to start after the first dose of study drug, as long as the available information does not conclusively indicate that the event emerged prior to the start date of the first cycle of study drug administration.

An overview of adverse events will present the number and percentage of safety population subjects who have at least one AE, at least one Grade 3 or higher AE, at least one treatment related AE, at least one serious AE, at least one AE of special interest, at least one AE leading to study drug withdrawal, at least one AE leading to death, and at least one treatment related AE leading to death, overall (subjects counted only once if any AE is experienced) and by highest NCI CTCAE grade (subjects counted only once at the highest grade level experienced).

The number and percentage of safety population subjects with AEs will be summarized by SOC and PT in total, and by highest NCI CTCAE grade. At each summary level, a subject will be counted only once if he/she experiences at least one AE, and when summarizing by highest NCI CTCAE grade, a subject will be counted only once at the highest grade level experienced. AE summary tables will be sorted by descending occurrence rate according to the SOC, and then by descending occurrence rate within PT. The following types of AE summaries will be prepared:

- All AE
- Grade  $\geq 3$  AE
- Onset date prior to date of surgery (Neoadjuvant Atezolizumab Therapy Phase only)
- Onset date on or after date of surgery, for safety population with surgery date (Neoadjuvant Atezolizumab Therapy Phase only)
- Treatment related AE
- Serious AE
- AE of special interest
- AE leading to death
- Treatment related AE leading to death
- AEs leading to study drug withdrawal

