S, E, P	Table 14.3.1.2c	Adverse Events With Onset On or After Date of Surgery by Highest NCI CTCAE Grade, Neoadjuvant Atezolizumab Therapy Phase	Safety Population With Surgery
S, E, P	Table 14.3.1.3.1	Grade $\geq 3$ Adverse Events by Highest NCI CTCAE Grade, Neoadjuvant Atezolizumab Therapy Phase	Safety Population

Interim Analysis Flag	Output Type and Number	Output Title	Output Population
	Table 14.3.1.3.2	Grade >=3 Adverse Events by Highest NCI CTCAE Grade, Surveillance/Survival Follow-up Phase	Safety Population
S, E, P	Table 14.3.1.4.1	Treatment Related Adverse Events by Highest NCI CTCAE Grade, Neoadjuvant Atezolizumab Therapy Phase	Safety Population
	Table 14.3.1.4.2	Treatment Related Adverse Events by Highest NCI CTCAE Grade, Surveillance/Survival Follow-up Phase	Safety Population
S, E, P	Table 14.3.1.4a	Treatment Related Adverse Events With Onset Prior to Date of Surgery by Highest NCI CTCAE Grade, Neoadjuvant Atezolizumab Therapy Phase	Safety Population
S, E, P	Table 14.3.1.4b	Treatment Related Adverse Events With Onset On or After Date of Surgery by Highest NCI CTCAE Grade, Neoadjuvant Atezolizumab Therapy Phase	Safety Population With Surgery
S, E, P	Table 14.3.1.5.1	Serious Adverse Events by Highest NCI CTCAE Grade, Neoadjuvant Atezolizumab Therapy Phase	Safety Population
	Table 14.3.1.5.2	Serious Adverse Events by Highest NCI CTCAE Grade, Surveillance/Survival Follow-up Phase	Safety Population
S, E, P	Table 14.3.1.5a	Treatment Related Serious Adverse Events by Highest NCI CTCAE Grade, Neoadjuvant Atezolizumab Therapy Phase	Safety Population
S, E, P	Table 14.3.1.5b	Serious Adverse Events With Onset Prior to Date of Surgery by Highest NCI CTCAE Grade, Neoadjuvant Atezolizumab Therapy Phase	Safety Population
S, E, P	Table 14.3.1.5c	Serious Adverse Events With Onset On or After Date of Surgery by Highest NCI CTCAE Grade, Neoadjuvant Atezolizumab Therapy Phase	Safety Population With Surgery
S, E, P	Table 14.3.1.6.1	Adverse Events of Special Interest by Highest NCI CTCAE Grade, Neoadjuvant Atezolizumab Therapy Phase	Safety Population
	Table 14.3.1.6.2	Adverse Events of Special Interest by Highest NCI CTCAE Grade, Surveillance/Survival Follow-up Phase	Safety Population
S, E, P	Table 14.3.1.7.1	Adverse Events Leading to Study Drug Withdrawal by Highest NCI CTCAE Grade, Neoadjuvant Atezolizumab Therapy Phase	Safety Population

Interim Analysis Flag	Output Type and Number	Output Title	Output Population

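### SAP 6.4.1 opens the Surveillance/Survival Follow-up adverse event window at the first dose of study drug, so neoadjuvant events of adjuvant-treated subjects enter both phases' tables

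*SAP*

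**What the plan says.** SAP 6.4.1 defines AEs separately for two phases.

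- **Neoadjuvant phase.** The window starts at the first dose of study drug. For continuing subjects it runs "through the day immediately preceding the start date of the first adjuvant cycle for subjects continuing in the Surveillance/Survival Follow-up Phase of the study".
- **Surveillance/Survival Follow-up Phase.** Here "an adverse event will be any event that starts following the start of the first dose of study drug for those subjects continued" in that phase. No sentence removes events already assigned to the neoadjuvant phase.

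The layout of the later-phase output is fixed by reference: "AEs in the Surveillance/Survival Follow-up Phase will be summarized and listed in the same form as aforementioned in the Neoadjuvant Atezolizumab Therapy Phase". The neoadjuvant text supplies two rules that this carries over:

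- the percentage base: "The number and percentage of safety population subjects with AEs will be summarized by SOC and PT in total";
- the grade rule, under which "a subject will be counted only once at the highest grade level experienced".

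A further summary is planned on top of the phase tables: "AE by highest NCI CTCAE grade will also be summarized for both study phases combined".

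**The concern.** Two windows that should meet at the first adjuvant cycle overlap completely for any subject who crosses it. The later-phase tables would then describe those subjects' whole time on study, not their time on adjuvant treatment.

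Safety and tolerability as adjuvant treatment is a stated objective (SAP Table 1). The later-phase AE tables are where a reader would look for it. If they carry events from the neoadjuvant doses and the surgical period, they cannot answer that question. The adjuvant experience would have to be rebuilt from the individual AE listing.

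**Working it through.** The plan states no AE rate or other figure for this point, so there is nothing to reproduce. The check compares the two definitions and then illustrates their effect.

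**1. The windows.** Take a subject with first neoadjuvant dose on date D and first adjuvant atezolizumab dose on a later date J.

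- Neoadjuvant window: D to J − 1.
- Later window as written: D onward.
- Overlap: D to J − 1, which is the entire neoadjuvant window.
- Union: D onward, which is the later window itself.

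So the subject's later-phase event set equals the both-phases set, and Table 14.3.1.2.2 repeats Table 14.3.1.2a for that subject. With the later window starting at J, the overlap is empty and the union is unchanged.

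**2. Does 'first dose' in the later definition mean the first adjuvant dose?** The wording is against it. The neoadjuvant paragraph uses the same phrase for the neoadjuvant start and names the first adjuvant cycle when it means that. The partial-date sentence is the same in both paragraphs. SAP 6.1.1 also uses the first cycle of study drug as the anchor for a single baseline shared by all phases.

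**3. Were separate windows intended?** Evidently yes. The neoadjuvant paragraph sets a hand-over date, SAP 3.1 labels adjuvant treatment as the Surveillance/Survival Follow-up Phase, and the combined summary is requested in addition to the phase tables.

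**4. Grades.** Each subject is counted once, at the highest grade. A Grade 3 event before surgery and a Grade 1 event on adjuvant treatment would put the subject at Grade 3 in the later-phase overview.

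**5. Partial dates.** SAP 6.1.2 imputes an onset date whenever the year is known, to settle treatment-emergent status. Its only special case is the first dose of study drug. The sentences in 6.4.1 also refer only to that dose. Nothing refers to the first adjuvant dose, so nothing decides the phase of an event whose possible dates straddle J.

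**6. Illustrative size.** Let r be the share of adjuvant-treated subjects with an event on or after J, and q the share with an earlier event. Both are assumed values, taken as independent.

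- Share of adjuvant-treated subjects counted, window as written: 1 − (1 − q)(1 − r).
- The same with all 180 planned patients as base: multiply by 50/180. The 50 is the planned adjuvant number in Protocol 4.1, and all 180 are taken as dosed.

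| r (target) | q | Window as written, base 50 | Window as written, base 180 |
|---|---|---|---|
| 10% | 20% | 28.0% | 7.8% |
| 10% | 80% | 82.0% | 22.8% |
| 20% | 50% | 60.0% | 16.7% |
| 40% | 50% | 70.0% | 19.4% |
| 60% | 80% | 92.0% | 25.6% |

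**7. Percentage base (secondary).** The SAP text names only the Safety Population, meaning any dose (SAP 5), for these tables, and Table 3 in SAP 7 carries the same label. The base alone would divide an adjuvant rate by 180/50 = 3.6, so one affected patient would show as 1/180 = 0.6% instead of 1/50 = 2.0%. If 'continued' means adjuvant-treated, no percentage could exceed 50/180 = 27.8%. The last column of the table shows window and base together: the result is above the target in the 10%/80% row and below it in the 60%/80% row.

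**The case against.** **It is a slip whose intent is plain.** The hand-over date is visible in the neoadjuvant paragraph, and a careful programmer might apply it to both phases. That is likely, but the SAP is the programming specification and its literal reading gives a different table. No other section removes the overlap.

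**Little depends on it.** The adjuvant phase is exploratory, all AEs are listed individually, and most of the affected tables carry no interim or primary-analysis flag in Table 3. The exception among the tables is 14.3.1.8.2, AEs leading to death, which is flagged for the primary analysis. This stands and limits the weight of the point.

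**The percentage base is not settled by the SAP text.** A reader might infer that adjuvant AE rates will be diluted 3.6-fold. The documents do not establish this. The shells are a separate file, and 'same form' may refer only to layout. Table 3 labels do not fix the base either: Table 14.1.1.2 is labelled All Enrolled Subjects, while SAP 6.2.1 bases its percentages on adjuvant-treated subjects. On the other side, the SAP does name a narrower base where it wants one: "Onset date on or after date of surgery, for safety population with surgery date" in 6.4.1, and "Safety Population With Surgery" in Table 3. That justifies a check of the shells, not a finding of dilution.

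**Partial dates.** A reader might also infer that the incomplete-date rules cause double counting by themselves. They do not: the imputation in SAP 6.1.2 would give most such events a single date, and as written the double placement comes mainly from the window. The rules need attention only because a corrected window needs a matching anchor.

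**Subgroups A and C.** It is tempting to say that their events simply remain in the neoadjuvant tables. SAP 6.4.1 does not say so. It speaks of subjects not continuing in the Surveillance/Survival Follow-up Phase, and SAP 6.2.1 summarises all four subgroups in that phase. Keeping their events in the neoadjuvant tables with no end date would also bring in SAEs from CT scans, blood draws and the optional biopsy, which Protocol 5.3.1 (with Table 5) and 5.4.2.2 collect throughout Surveillance.

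**Conclusion.** The window is wrong as written. For every subject who receives adjuvant atezolizumab, all neoadjuvant events enter both phases' tables and can set the grade shown in the later one. This rests on the SAP wording alone.

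Its size cannot be given, because the documents contain no event rates for this setting. The table above shows only that the effect could be large under assumed rates. If the shells also use the full Safety Population, the base works in the opposite direction, so neither inflation nor dilution of the reported adjuvant rate can be claimed.

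Two matters are open for the sponsor, not errors with a known answer:

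- whether 'continuing' means adjuvant-treated, as SAP 3.1 and the hand-over date suggest, or entering Surveillance, as SAP 6.2.1 suggests;
- where AEs of Subgroups A and C after surgery are reported. If 'continuing' means entering Surveillance, these subjects have no adjuvant cycle and so no stated end to their neoadjuvant window.

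The primary efficacy analysis, the interim safety rule, the combined-phase AE table and the listing of all AEs are unaffected. The correction should be made before the later-phase AE tables are programmed.

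**What to change.** 1. In SAP 6.4.1, Surveillance/Survival Follow-up Phase, start the AE window for adjuvant-treated subjects (Subgroups B and D) on the date of the first adjuvant atezolizumab dose.
2. Add that dose as a second anchor in the partial-date rules of SAP 6.1.2 and of both phase paragraphs in 6.4.1, so that each event falls in one phase only.
3. Define 'continuing'. State where post-surgery AEs of Subgroups A and C are reported, including SAEs from Surveillance procedures.
4. Check the shells. If they use the Safety Population as the percentage base, use subjects with at least one adjuvant dose for the adjuvant AE tables, as SAP 6.2.1 does for adjuvant disposition.

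The cost is SAP wording and, for item 4, possibly the table shells. No new data are needed and patient management does not change.

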#### **6.4.2 Laboratory Parameters**

Serum chemistry and hematology parameters will be converted to a standard set of units to be agreed upon with the sponsor.

##### Neoadjuvant Atezolizumab Therapy Phase

Converted laboratory parameter values will be summarized descriptively (n, mean, standard deviation, median, minimum, and maximum) for safety population subjects at each scheduled data collection time point. Change from baseline (the latest value collected prior to first dose) to each scheduled data collection time point will also be summarized descriptively for safety population subjects.

Shift tables will present a cross tabulation of baseline results categories (values falling in low, normal, high categories relative to normal ranges, or values being associated with grades) versus result categories at each follow up visit. The number and percentage of safety population subjects falling within each cross tabulation cell will be presented; the denominator for each percentage will be the number of safety population subjects with a baseline result and a follow-up result at the given visit for the given parameter.

##### Surveillance/Survival Follow-up Phase

Same analysis will be done for the Surveillance/Survival Follow-up Phase using the same baseline as the Neoadjuvant Atezolizumab Therapy Phase.

#### **6.4.3 Vital Signs**

Vital signs will be summarized descriptively (n, mean, standard deviation, median, minimum, and maximum) for safety population subjects at each scheduled data collection time point. Raw and change from baseline vital sign values, including systolic and diastolic blood pressure, heart rate, height, weight, body temperature for both oral and auricular, and respiratory rate, will be summarized using descriptive statistics at baseline and each assessment time point at post-dose visits for each of the two study phases.

#### **6.4.4 Physical Examination**

Complete physical examination at screening and limited physical examination at each scheduled data collection time point will be listed for both phases of the study.

#### **6.4.5 Pulmonary Function Test**

Raw and change from baseline for pulmonary function test will be summarized descriptively (n, mean, standard deviation, median, minimum, and maximum) and listed at each scheduled data collection time point for the Neoadjuvant Atezolizumab Therapy Phase.

#### 6.4.6 ECOG Performance Status

Number and percentage for each ECOG performance status will be summarized and listed at each scheduled data collection time point for both phases of the study.

#### 6.4.7 Analyses of Other Safety Assessments

The data for coagulation (aPTT and INR) tests, Pregnancy test, urinalysis, thyroid function test (TSH, Free T3 and Free T4), C-reactive protein, viral serology will be listed.

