As of the 1 December 2015 data cutoff date, 659 patients with NSCLC have been treated with atezolizumab as a fixed dose of 1200 mg IV q3w. In Study GO28754, 93.8% patients experienced at least one adverse event, 65% of patients experienced one treatment-related adverse event, and 12% of patients experienced Grade ≥ 3 treatment-related adverse event.

Single-Agent Clinical Safety in Patients with Non-Small Cell Lung Cancer in Study GO28915 (OAK)

As of the July 2016 data cutoff date, 609 patients with NSCLC were treated with atezolizumab as a fixed dose of 1200 mg IV q3w and 578 patients were treated with docetaxel 75 mg/m² IV q3w in Study GO28915. Fewer patients in the atezolizumab arm (37%) experienced Grade 3–4 adverse events compared with the docetaxel arm (54%). For Grade 3–4 adverse events that were assessed as treatment-related, the difference was greater between the two arms (15% vs. 43%, respectively). Rates of immune-mediated adverse events were low in patients treated with atezolizumab—pneumonitis (1%), hepatitis (0.3%), and colitis (0.3%). Adverse event-related discontinuation rates were 8% with atezolizumab arm vs. 19% for docetaxel arm.

For additional information, refer to the Atezolizumab Investigator's Brochure.

Single-Agent Clinical Safety in Patients Undergoing Surgery

Based on the mechanism of action and known safety profile of atezolizumab, no major complications (pre or post-surgery) are anticipated. The most commonly reported immune-mediated events with atezolizumab are dermatologic reactions and laboratory abnormalities (changes in liver function tests and thyroid function tests). Given the protocol design, short timeframe from atezolizumab administration to surgery, and the known longer time to onset of such events, these events are considered unlikely in the Neoadjuvant Atezolizumab Therapy Phase of this study (see Section 1.3).

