5.1.1 Risks Associated with Atezolizumab

Atezolizumab has been associated with risks such as the following: infusion-related reactions (IRRs) and immune-mediated hepatitis, pneumonitis, colitis, pancreatitis, diabetes mellitus, hypothyroidism, hyperthyroidism, adrenal insufficiency, hypophysitis, Guillain-Barré syndrome, myasthenic syndrome or myasthenia gravis, meningoencephalitis, myocarditis, nephritis, myositis, and severe cutaneous adverse reactions. Immune-mediated reactions may involve any organ system and may lead to hemophagocytic lymphohistiocytosis (HLH) and macrophage activation syndrome (MAS), which are considered to be potential risks for atezolizumab.

Refer to [Appendix 9](#) of the protocol and Section 6 of the Atezolizumab Investigator's Brochure for a detailed description of anticipated safety risks for atezolizumab.

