  - ee Includes specific gravity, pH, glucose, protein, ketones, and blood.
  - ff Perform thyroid function tests at baseline, the pre-surgery visit, at post-surgery visit and then approximately every 9 weeks (3 cycles) during adjuvant atezolizumab treatment in the Adjuvant Atezolizumab Therapy Phase.
  - gg Viral serology includes HIV, Hepatitis B (HBsAg, antibodies against HBsAg, hepatitis B core antigen; HBV DNA is required positive anti-HBc antibody test), and HCV antibody (anti-HCV).
  - hh See [Appendix 3](#) for detailed schedule.
  - ii Tumor tissue may be archival; it does not need to be collected within 42 days of enrollment.
  - jj Tissue biopsy (tumor and lymph node, if available); at disease progression/recurrence is optional and requires a separate ICF signature. Tissue collection by CNB is preferred, however collection by EBUS, or bronchoscopy are acceptable alternatives.
  - kk The biomarker blood sample may be collected up to 7 days prior to the visit. *Whole blood sample for biomarker assessments should preferably be collected on the day of surgery (prior to surgery and prior to antibiotic administration). It is acceptable to collect the sample up to 7 days prior to surgery (including the day of surgery, and prior to antibiotic administration). If sample needs to be collected outside of the recommended window, please contact the Medical Monitor for guidance and approval.*
  - ll Plasma, serum and, at selected timepoints, also PBMCs will be collected (see [Appendix 2](#)).
  - mm Biomarker blood samples will be collected approximately at every 6 weeks to 3 months but can be adjusted to synchronize with Surveillance visits (See [Appendix 2](#)).
  - nn Encouraged for patients undergoing EBUS and/or bronchoscopy. See lab manual for exact nomenclature and specific areas to be sampled during procedure.
  - oo Should be performed after approximately 3-4 months of first adjuvant atezolizumab treatment.
  - pp In the Neoadjuvant Atezolizumab Therapy Phase, neoadjuvant treatment with atezolizumab 1200 mg will be given q21d for a maximum of 2 cycles. In Adjuvant Atezolizumab Therapy Phase, adjuvant treatment with atezolizumab 1200 mg will be given q21d for maximum of 12 months (maximum 17 cycles). Patients may need to remain in the clinic post-infusion for monitoring if needed. See Section 4.3.2 for administration instructions.

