	Table 14.3.1.7.2	Adverse Events Leading to Study Drug Withdrawal by Highest NCI CTCAE Grade, Surveillance/Survival Follow-up Phase	Safety Population
P	Table 14.3.1.8.1	Adverse Events Leading to Death, Neoadjuvant Atezolizumab Therapy Phase	Safety Population
P	Table 14.3.1.8.2	Adverse Events Leading to Death, Surveillance/Survival Follow-up Phase	Safety Population
S, E, P	Table 14.3.1.9.1	Treatment Related Adverse Events Leading to Death, Neoadjuvant Atezolizumab Therapy Phase	Safety Population
	Table 14.3.1.9.2	Treatment Related Adverse Events Leading to Death, Surveillance/Survival Follow-up Phase	Safety Population
S, E, P	Listing 14.3.2.1.1	Listing of Adverse Events Leading to Death, Neoadjuvant Atezolizumab Therapy Phase	Safety Population
P	Listing 14.3.2.1.2	Listing of Adverse Events Leading to Death, Surveillance/Survival Follow-up Phase	Safety Population
S, E, P	Listing 14.3.2.2.1	Listing of Serious Adverse Events, Neoadjuvant Atezolizumab Therapy Phase	Safety Population
	Listing 14.3.2.2.2	Listing of Serious Adverse Events, Surveillance/Survival Follow-up Phase	Safety Population
S, E, P	Listing 14.3.2.3.1	Listing of Adverse Events Leading to Study Drug Withdrawal, Neoadjuvant Atezolizumab Therapy Phase	Safety Population
	Listing 14.3.2.3.2	Listing of Adverse Events Leading to Study Drug Withdrawal, Surveillance/Survival Follow-up Phase	Safety Population
S, P	Table 14.3.3.1.1	Serum Chemistry Values Over Time, Neoadjuvant Atezolizumab Therapy Phase	Safety Population
	Table 14.3.3.1.2	Serum Chemistry Values Over Time, Surveillance/Survival Follow-up Phase	Safety Population
S, P	Table 14.3.3.2.1	Hematology Values Over Time, Neoadjuvant Atezolizumab Therapy Phase	Safety Population
	Table 14.3.3.2.2	Hematology Values Over Time, Surveillance/Survival Follow-up Phase	Safety Population
	Table 14.3.3.3.1	Shift Table of Serum Chemistry Values, Neoadjuvant Atezolizumab Therapy Phase	Safety Population
	Table 14.3.3.3.2	Shift Table of Serum Chemistry Values, Surveillance/Survival Follow-up Phase	Safety Population
	Table 14.3.3.4.1	Shift Table of Hematology Values, Neoadjuvant Atezolizumab Therapy Phase	Safety Population

Interim Analysis Flag	Output Type and Number	Output Title	Output Population
	Table 14.3.3.4.2	Shift Table of Hematology Values, Surveillance/Survival Follow-up Phase	Safety Population
P	Table 14.3.4.1	Vital Sign Values Over Time, Neoadjuvant Atezolizumab Therapy Phase	Safety Population

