P	Listing 16.2.6.11	Post Neoadjuvant Treatment Surgery	Efficacy Population
	Listing 16.2.6.12	Adjuvant Chemotherapy	Efficacy Population
	Listing 16.2.6.13	Cancer Radiotherapy	Efficacy Population
	Listing 16.2.6.14	Survival and Recurrence Follow-up	Efficacy Population
	Listing 16.2.6.15	Listing of Individual Efficacy Data	Efficacy Population
S, E, P	Listing 16.2.7.1	Listing of Adverse Events	Safety Population
S, E, P	Listing 16.2.7.2	Listing of Serious Adverse Event Details	Safety Population
	Listing 16.2.8.1	Listing of Serum Chemistry	Safety Population
	Listing 16.2.8.2	Listing of Hematology	Safety Population
	Listing 16.2.8.3	Listing of Vital Signs	Safety Population
	Listing 16.2.8.4	Complete Physical Examination	Safety Population
	Listing 16.2.8.5	Pulmonary Function Tests	Safety Population
	Listing 16.2.8.6	ECOG Performance Status	Safety Population
	Listing 16.2.8.7	Other Safety Assessments	Safety Population
P	Figure 1.1	Forest Plot of Major Pathological Responders	Efficacy Population
P	Figure 1.2.1	Kaplan – Meier Plot for Overall Survival	Efficacy Population
P	Figure 1.2.2	Kaplan – Meier Plot for Disease-Free Survival	Primary Efficacy Population
P	Figure 1.2.3	Kaplan – Meier Plot for Event-Free Survival	Efficacy Population
P	Figure 1.2.4	Kaplan – Meier Plot for Overall Survival by Major Pathologic Responder	Efficacy Population
P	Figure 1.2.5	Kaplan – Meier Plot for Disease-Free Survival by Major Pathologic Responder	Primary Efficacy Population
P	Figure 1.2.6	Kaplan – Meier Plot for Event -Free Survival by Major Pathologic Responder	Efficacy Population

Interim Analysis Flag	Output Type and Number	Output Title	Output Population
P	Figure 1.2.7	Kaplan – Meier Plot for Overall Survival by PD-L1 Subgroup	Efficacy Population
P	Figure 1.2.8	Kaplan – Meier Plot for Disease-Free Survival by PD-L1 Subgroup	Primary Efficacy Population
P	Figure 1.2.9	Kaplan – Meier Plot for Event -Free Survival by PD-L1 Subgroup	Efficacy Population

Note: Interim analysis flags are S = Safety Interim Analysis and E = Efficacy Interim Analysis. P = Primary Analysis.

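### SAP 6.4.7 lists TSH, free T3 and free T4 without summarising them; a shift table and any-high / any-low TSH counts would be a cheap, optional safety-reporting improvement

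*SAP*

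**What the plan says.** SAP 6.4.7 groups thyroid function with coagulation, pregnancy test, urinalysis, C-reactive protein and viral serology, and plans a listing for all of them: "thyroid function test (TSH, Free T3 and Free T4), C-reactive protein, viral serology will be listed". In SAP Table 3 the data appear only in Listing 16.2.8.7, titled "Other Safety Assessments".

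The SAP schedule (Section 4, footnote ff) reads "Perform thyroid function tests at baseline, the pre-surgery visit, at post-surgery visit and then approximately every 9 weeks (3 cycles") during adjuvant treatment. Protocol Appendix 1 has the same schedule.

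Serum chemistry and hematology are handled differently. SAP 6.4.2 gives them unit conversion, by-visit statistics, change from baseline, and shift tables: "Shift tables will present a cross tabulation of baseline results categories". Table 3 carries the matching outputs, for example "Serum Chemistry Values Over Time, Neoadjuvant Atezolizumab Therapy Phase".

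On risk, Protocol 5.1.1 includes "diabetes mellitus, hypothyroidism, hyperthyroidism, adrenal insufficiency, hypophysitis" in its list. Protocol 1.2.2.1 counts "laboratory abnormalities (changes in liver function tests and thyroid function tests") among the immune-mediated findings most often reported, and then says of such events in surgical patients that "these events are considered unlikely in the Neoadjuvant Atezolizumab Therapy Phase of this study".

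**The concern.** A listing suits a test done once at screening. It suits a repeated test less well, because the reader has to build the rate by hand. Here the repeated test tracks a known effect of the drug, and the protocol makes a background statement that such effects should be uncommon before surgery. The trial schedules blood tests that bear directly on that statement, but no planned output turns them into a number or percentage of patients. What is at stake is completeness of the thyroid safety picture, chiefly hypothyroidism in patients who receive no adjuvant atezolizumab.

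**Working it through.** The plan gives no thyroid rate, so there is no figure to reproduce. The check is a cross-reading plus one timing calculation.

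**1. Which tests in SAP 6.4.7 are repeated.** In both schedules, coagulation, pregnancy test, urinalysis, C-reactive protein and viral serology have one scheduled collection, at screening, and none after baseline. Thyroid function has 2 scheduled post-baseline tests around surgery. A patient given all 17 adjuvant cycles in the schedule has about 6 more, if tested at Cycles 1, 4, 7, 10, 13 and 16. Unmarked tests may be done as standard of care, so *repeated* here means repeated by schedule.

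**2. Whether thyroid results enter another summary.** The chemistry panel contains no TSH, T3 or T4, and SAP 6.4.2 covers only chemistry and hematology. Table 3 has:
- chemistry, 4 tables: 14.3.3.1.1, 14.3.3.1.2, 14.3.3.3.1, 14.3.3.3.2;
- hematology, 4 tables: 14.3.3.2.1, 14.3.3.2.2, 14.3.3.4.1, 14.3.3.4.2;
- thyroid, 0 tables and 1 listing.

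**3. What the AE tables capture.**
- Hypothyroidism: Protocol Appendix 9 directs replacement hormone even without symptoms. Under Protocol 5.3.5.5 a medical intervention makes the abnormality a reportable AE, within the reporting window.
- Low TSH: Appendix 9 calls 0.1 to <0.5 mU/L asymptomatic hyperthyroidism. Appendix 10 names hyperthyroidism as an AESI, and AESIs are reported to 90 days after the last dose.
- Subgroups B and D: Table 5 footnote a keeps reporting open between the neoadjuvant and adjuvant phases.
- Subgroups A and C: Table 5 ends non-serious AE reporting 30 days after the last neoadjuvant dose. Hypothyroidism is absent from Appendix 10, so the 90-day window does not cover it when non-serious. Protocol 5.6 (later events) also covers only serious AEs and AESIs.

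**4. When the post-surgery test falls, for patients given both doses.** Inputs from Appendix 1: dose 2 on Day 22 + d, with d from -3 to 3; surgery on Day 40 ± 10; post-surgery visit 28 to 42 days after surgery. Footnote i moves later visits when dose 2 is late.

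Gap = surgery day + visit interval - dose 2 day.

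- Windows at face value: minimum 30 + 28 - 25 = 33; maximum 50 + 42 - 19 = 73.
- With footnote i: minimum (30 + d) + 28 - (22 + d) = 36, for d of 0 or more; the maximum stays 73, at d = -3.
- Version 3 schedule (Appendix 11; visit 23 to 37 days after surgery): 30 + 23 - 25 = 28 to 50 + 37 - 19 = 68 at face value. With the same footnote the minimum is (30 + d) + 23 - (22 + d) = 31, so 31 to 68.
- Pre-surgery test (Day 36 ± 3): 33 - 25 = 8 to 39 - 19 = 20 at face value. With the footnote the minimum is (33 + d) - (22 + d) = 11, so 11 to 20.

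With the footnote applied, every on-window post-surgery test falls after day 30 and before day 90 under both schedules. The pre-surgery test is always inside the 30-day window.

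**5. The conflict in the AE rules.** Appendix 1 marks AEs at the post-surgery visit, and Protocol 5.3.1 refers to AEs of the surgery phase. The same 5.3.1, Table 5 and Appendix 1 footnote rr set the 30-day limit. SAP 6.4.1 puts no 30-day end on neoadjuvant-phase AEs and plans tables for onset on or after surgery, so a late event that a site records is counted. Whether sites record it is what the documents leave open.

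**The case against.** The case against is strong on consequence. The protocol's safety endpoint is AE incidence graded by CTCAE, and no section promises a laboratory rate for thyroid tests, so nothing is contradicted. The listing keeps every value, and a rate could be derived later. The Subgroup A and C gap comes from the protocol's AE window, which an SAP change leaves in place. All of that stands, and it limits the point to an improvement in reporting.

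Three stronger readings are tempting, and the documents do not support them.
- *Thyroid dysfunction would go unreported.* It would not. The AE and AESI tables cover treated, symptomatic or clinically significant events, and Protocol 5.3.5.5 lets the investigator's judgment alone make an abnormality reportable.
- *Mildly low TSH, monitored but not treated, would be missed.* The protocol labels that state hyperthyroidism, which is an AESI with no stated grade threshold, and on-window post-surgery tests fall within its 90 days. One could argue that a bare TSH value must first qualify as an AE, but the labelling points the other way.
- *The unflagged listing shows thyroid data were singled out for omission at the interims.* Of the 8 chemistry and hematology tables, 6 are also unflagged in Table 3 as extracted. Only 14.3.3.1.1 and 14.3.3.2.1 carry flags (S, P), and the chemistry and hematology listings have none.

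**Conclusion.** The point holds as a cheap, optional improvement and is not an error in the plan. The only repeated test in SAP 6.4.7 is listed and never counted, for a named risk. Two kinds of finding may escape the AE tables: untreated, asymptomatic change judged not clinically significant; and, in Subgroups A and C, non-serious hypothyroidism first seen at the post-surgery test, 36 to 73 days after dose 2 (31 to 68 under the Version 3 schedule). The second rests on patients having received both doses, visits falling on window, footnote i being applied, and sites following the 30-day limit where the documents conflict. The size of the gap cannot be estimated, because the documents give no thyroid event rate. The primary analysis and the stopping rules are unaffected.

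**What to change.** Move TSH, free T3 and free T4 from SAP 6.4.7 to 6.4.2, and extend the unit conversion there to these analytes. For each phase, using the same baseline as chemistry, provide:
- a low / normal / high shift table against the local laboratory range;
- the number and percentage of patients with any post-baseline high TSH and, separately, any post-baseline low TSH, by baseline TSH category. The split matters because Protocol 4.1.2 admits patients on stable thyroid replacement.

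By-visit change from baseline is optional. In Table 3, flag the neoadjuvant-phase thyroid table S, P, like chemistry Table 14.3.3.1.1.

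The cost is SAP wording, a few tables, a little new code for the any-high and any-low counts, and handling of local units and ranges, because Protocol 4.5.8 sends these tests to local laboratories. Protocol 9.4 says that local ranges are collected. No protocol change or extra site work is needed.
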